5.3.2 HANDLING OF PARTICPANT WITHDRAWALS OR TERMINATION

Approximately 30 subjects will be enrolled in the study. Subjects will be encouraged to complete the study and all assessments. However, subjects may voluntarily withdraw at any time, and the investigator may discontinue individual subjects from the study at any time. For subjects who withdraw consent from the study, no study procedures will be done thereafter. For those that withdraw from receiving the study agent, follow-up visits and the safety phone follow-up are to occur as per the protocol. Excluding cases of medical emergency, but prior to the discontinuation of a subject from the clinical study for disease worsening, the study investigator should discuss each case of discontinuation with the sponsor and/or the medial monitor.

The subject withdrawal criterion below should be used to assess worsening or disease progression. In such cases, a documented assessment by the principle investigator is required, and subjects with clinically significant disease progression should be considered for withdrawal from the study and subsequent initiation of standard of care:

- A BCVA loss of ≥ 5 letters from baseline
- New macular subretinal hemorrhage
- Investigator discretion based on acute worsening of underlying disease or substantial risk to further participation in the study

5.4 PREMATURE TERMINATION OR SUSPENSION OF STUDY

Both the sponsor and the investigator reserve the right to terminate the study at any time. Should this be necessary,

both parties will arrange discontinuation procedures and notify the appropriate regulatory authority(ies), IRBs, and IECs. In terminating the study, the sponsor and the investigator will continue to protect the subjects’ privacy and identity as required by relevant statues and regulations.

Alkahest, Inc. has the right to terminate a study site from participating in the study at any time. Reasons for study or site termination may include, but are not limited to:

- Unsatisfactory subject enrollment (i.e., < 2 subjects enrolled within a 6-month period)
- Unacceptable protocol deviations/violations as assessed by the medical monitor
- Inaccurate or incomplete data entry and recording
- Investigational site non-compliance with ICH/GCP
- Unacceptable emergent safety profile

6 TREATMENTS

6.1 STUDY AGENT DESCRIPTION

6.1.1 ACQUISITION

The study agent will be manufactured, labeled, packaged, and distributed by Alkahest, Inc.

6.1.2 FORMULATION, APPEARANCE, PACKAGING, AND LABELING

[REDACTED] The subjects will be provided with 1 bottle at each treatment visit so that the time windows between visits (see [Section 15.1, Schedule of Events Table](#)) will be covered. The study agent will be delivered to the sites immediately prior to site activation and thereafter upon request. The product will be labeled for investigational use according to the relevant regulatory requirements for clinical studies.

For further details and information on ALK4290, including packaging and labeling, see the [REDACTED].

6.1.3 PRODUCT STORAGE AND STABILITY

[REDACTED] A temperature log must be maintained to make certain the study agent is stored at the correct temperature. If the storage conditions are found to be outside the specified range, the site must immediately notify the sponsor or designee.

6.1.4 DOSING AND ADMINISTRATION

The study agent will be self-administered orally twice daily for a total daily dose of 800 mg. Training on study agent administration will be conducted prior to initial study agent administration (at Visit 2) under the supervision of study personnel. All study agent administrations at the study site will be done under the direct supervision of the study personnel for documentation of precise administration times.

6.2 STUDY AGENT ACCOUNTABILITY

The investigator and/or pharmacist will receive the study agent delivered by the sponsor when the following requirements are fulfilled:

- Approval of the study protocol and Informed Consent by the IRB or IEC
- Availability of a signed and dated clinical trial contract between the sponsor and the investigational site
- Approval/notification of the appropriate regulatory authority
- Availability of the curriculum vitae of the principal investigator
- Availability of a signed and dated clinical trial protocol or immediately imminent signing of the clinical trial protocol

The investigator and/or pharmacist must maintain records of the study agent’s delivery to the trial site, the inventory at the site, the use by each subject, and the return to the sponsor or alternative disposition of unused study agent.

These records will include dates, quantities, batch/serial numbers, expiry (‘use by’) dates, and the unique code numbers assigned to the study agent and trial subjects. The investigator/pharmacist will maintain records that document adequately that the subjects were provided the doses specified by the protocol and reconcile all study agent received from the sponsor. At the time of final study agent reconciliation, the investigator/pharmacist must verify that all unused or partially used portion of study agent have been returned by the clinical trial subject and that no remaining study agent is retained by the investigator.

Accountability records must be maintained and readily available for inspection by representatives of Alkahest, Inc. or their designee and are open to inspection by regulatory authorities at any time. The accounts of any study agent accidentally wasted or intentionally disposed of must be maintained.

The disposal of used, partially used, or wasted study agent materials must be performed in accordance with the institution’s drug disposal policy. At study initiation, the clinical study monitor will evaluate the site’s standard operating procedure for study drug disposal/destruction to ensure it complies with study requirements. At the end of the study, following final study agent reconciliation by the monitor, the study site will be instructed by the sponsor to return or destroy all unused study agent supplies, including empty containers. A copy of the institution’s drug disposal policy should be maintained or referenced in the ISF.

6.3 CONCOMITANT MEDICATIONS AND TREATMENTS

All prescription, over-the-counter, and non-prescription medications (including herbal therapies and supplements) must be documented in the source documents and electronic Case Report Forms (eCRFs). All subjects should be maintained on the same medications at the same dosage and administration throughout the entire study period, as medically feasible, with no introduction of new chronic therapies. Any changes in medications should be documented in the eCRF with reason for change (e.g., adverse event, etc.).

6.4 PROHIBITED TREATMENTS, MEDICATIONS, AND PROCEDURES

No other interventional therapy for wAMD is concomitantly allowed.

The use of oral corticosteroids or high potency topical steroids (e.g. with systemic exposure) are restricted during the screening and treatment period of the study. The use of inhaled corticosteroids will be allowed if stably treated for 4 weeks prior to screening without a dose adjustment and not anticipated to require a dose adjustment during the study treatment period. The use of low potency topical corticosteroids (other than those intended for ocular application) will be allowed.

Primarily, no changes in concomitant therapy will be allowed except for treatments permitted according to [Section 6.3](#) above. However, in case of adverse events in need of treatment, symptomatic therapy according to the judgement of the investigator will be permitted. All concomitant therapies and/or rescue therapies will be recorded on the appropriate pages of the eCRF.

[REDACTED] Subjects should be advised to avoid alcoholic beverages from 48 hours before study agent administration and until the end-of-study examination.

7 VARIABLES AND THEIR ASSESSMENT

For the following endpoints, baseline is the value from Visit 2 and if not measured at Visit 2, then is the value from Visit 1. Detailed information on the methodology used with the following will be included in a Statistical Analytical Plan (SAP).

7.1 THERAPEUTIC EFFECT

BCVA will be assessed using ETDRS charts at 4 meters initial testing distance. The trained technician measuring the BCVA using ETDRS should be the same throughout the study period. A detailed manual for performing refractions and measuring BCVA using the ETDRS testing method will be provided to investigators.

7.2 SAFETY AND EXPLORATORY OUTCOMES

Safety will be assessed by the incidence and intensity of adverse events (AEs) (see [Section 7.2.1](#)). Changes in laboratory test results, vital signs, ECG, physical examination, and/or ocular morphologic investigations will be recorded as AEs/serious adverse events (SAEs) in the eCRF if they are judged clinically relevant by the investigator.

7.2.1 ASSESSMENT OF ADVERSE EVENTS

7.2.1.1 Terminology for Use for Adverse Event Descriptions

When reporting an adverse event, the event description should use the best matching terminology describing the event as found in the Common Terminology Criteria for Adverse Events (CTCAE v4.03). If an available CTCAE term fits the event well, no additional descriptors may be needed. However, necessary descriptions should be added in order to clarify the event or to place it in an appropriate context. The adverse event name should ideally be 1-3 words in length with additional description provided elsewhere on the adverse event report. A copy of the CTCAE is provided in the ISF. Standardized terms from the CTCAE will be used by the sponsor and the Contract Research Organization (CRO) to categorize events for reporting to regulatory authorities using the Medical Dictionary for Regulatory Activities (MedDRA, v. 20.1). In most cases, the CTCAE terms match MedDRA coding terminology. If an appropriate term matching the adverse event cannot be found in the CTCAE and the

preferred MedDRA term is unknown, the AE description should include a diagnosis, sign, or symptom with additional information to facilitate subsequent categorization into MedDRA coding terms.

7.2.1.2 Definition of Adverse Events

7.2.1.2.1 Adverse Event

An AE is defined in the ICH E2D as “any unfavorable or unintended sign, symptom, or disease temporarily associated with the use of a medicinal product whether or not considered related to the product.” Progression or worsening of the medical condition under study, by itself, does not necessarily constitute an adverse event unless the change can be reasonably attributed to an action of the study agent and not only to its lack of efficacy. Simply defining an adverse event does not imply a causal relationship; relatedness to the study agent is defined in [Section 7.2.1.2.4](#).

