7.2.1.2.5 Worsening of Underlying Disease and/or Other Pre-Existing Conditions

Worsening of the underlying disease and/or of other pre-existing conditions will be recorded as an AE/SAE in the eCRF.

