7.2.1.2.6 Changes in Safety Evaluations

Changes in vital signs, ECG, physical examination, laboratory test results, and ophthalmic evaluations will be recorded as an AE/SAE in the eCRF if they are judged clinically relevant by the investigator.

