7.2.1.2.7 Adverse Events of Special Interest

The following are considered adverse events of special interest (AESI):

- Hepatic injury defined by the following alterations of liver parameters:
For subjects with normal liver function at baseline an elevation of AST and/or ALT \geq 3-fold ULN combined with an elevation of total bilirubin \geq 2-fold upper limit of normal (ULN) measured in the same blood draw sample. Subjects showing these lab abnormalities need to be followed up according to [Section 17.1.2](#).
- Abrupt decrease ($>$ 15 letters lost from baseline) of BCVA
- QTc prolongation ($>$ +50 ms from baseline and $>$ 450 ms)

Protocol-specific AESIs are to be reported in an expedited manner similar to SAEs even if they do not meet any of the criteria for an SAE (see [Section 7.2.1.2.2](#)).

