8.3 Evaluable Set

The Evaluable set includes all subjects who complete at least 3 weeks of treatment during the 6-week treatment period.

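### No planned post-baseline BCVA summary includes subjects who stop before 3 weeks, and two protocol sections word the recording of wet AMD worsening differently

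*Protocol*

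**What the plan says.** **BCVA summaries.** SAP 8.3 defines the main efficacy set: "The Evaluable set includes all subjects who complete at least 3 weeks of treatment during the 6-week treatment period". SAP 8.4 makes the Per Protocol (PP) set a subset of it. SAP 8 says the efficacy analyses need not be confined to these two sets, but the outputs listed in SAP 24 to 26 are:

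| Output | Content | Set |
|---|---|---|
| Table 14.2.1.1 | BCVA and change by visit | Evaluable |
| Table 14.2.1.2 | BCVA and change by visit | PP |
| Table 14.2.1.3 | Change in categories | Evaluable |
| Figure 14.2.1 | Box plot by visit | Evaluable |
| Listing 16.2.6.1 | Individual scores | ITT |

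SAP 6 allows subjects who stop before Day 22 to be replaced (Protocol 10.5 puts the cut at Visit 4). Under Protocol 5.3.2, a loss of 5 or more letters is one prompt for a documented assessment of worsening, and "subjects with clinically significant disease progression should be considered for withdrawal from the study and subsequent initiation of standard of care".

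**Recording of worsening.** Protocol 7.2.1.2.1 says "Progression or worsening of the medical condition under study, by itself, does not necessarily constitute an adverse event", with the qualification "unless the change can be reasonably attributed to an action of the study agent and not only to its lack of efficacy". Protocol 7.2.1.2.5 carries no such qualification: "Worsening of the underlying disease and/or of other pre-existing conditions will be recorded as an AE/SAE in the eCRF". Protocol 7.2.1.2.6 adds that changes in several safety measures and "ophthalmic evaluations will be recorded as an AE/SAE in the eCRF if they are judged clinically relevant by the investigator". Protocol 7.2.1.2.7 makes an abrupt loss of more than 15 letters an adverse event of special interest (AESI).

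**The concern.** BCVA change is the primary endpoint, and BCVA loss is itself a listed prompt for withdrawal. Leaving out subjects who stop before 3 weeks is therefore not neutral: the outcome being summarised can decide who is summarised. Replacement can restore the number in the tables, so a shortfall need not show there. In a single-arm study compared with zero, no control group is subject to the same selection.

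The AE tables use the Safety set and would be the natural place to see these subjects' worsening. AE incidence, seriousness and severity are also the only secondary endpoint (SAP 3.2). Yet the two protocol sections do not agree on whether worsening due only to lack of efficacy has to be recorded.

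**Working it through.** **Step 1. Count the summaries.** Post-baseline BCVA outputs other than the listing: 3 tables + 1 figure = 4. On the Evaluable set: 3. On the PP set: 1. On the Safety or ITT set: 0. Baseline BCVA is in the ITT demography table (SAP 11.2, Table 14.1.2), but that table carries no change from baseline.

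**Step 2. Check whether the data exist.** BCVA is scheduled at Visits 3 to 10, so there are 8 post-baseline visits. Under Protocol 8.2.3, subjects who stop only the agent still have end-of-treatment procedures and follow-up visits, and BCVA is measured at Visits 8, 9 and 10. The values are collected and listed; they are not summarised.

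**Step 3. Try to size the effect.** SAP 6 gives 30 enrolled and about 25 evaluable: 30 − 25 = 5 subjects. No reason is attached to those 5. The documents give no rate of progression withdrawal, no expected BCVA change and no standard deviation, so no estimate is possible.

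The following shows only how the arithmetic behaves. Assume an Evaluable mean change m = 0 with n = 25, and k early stoppers with mean change c. The mean over all is (25m + kc)/(25 + k):

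| c (assumed) | k = 1 | k = 3 | k = 5 |
|---|---|---|---|
| −5 | −0.19 | −0.54 | −0.83 |
| −10 | −0.38 | −1.07 | −1.67 |
| −15 | −0.58 | −1.61 | −2.50 |

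For example, k = 5 and c = −10 gives −50/30 = −1.67 letters. The values of m, c and k are all assumed. If early stoppers had not lost vision, the shift would vanish or reverse. With replacement, k could exceed 5.

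**Step 4. Set the recording rules side by side.**

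| Worsening of wet AMD | 7.2.1.2.1 | 7.2.1.2.5 | Other provision |
|---|---|---|---|
| Attributable to the agent | May be an AE | Recorded | Not needed |
| Lack of efficacy only, abrupt loss > 15 letters | Not necessarily an AE | Recorded | AESI, Table 14.3.5 (Safety set) |
| Lack of efficacy only, judged clinically relevant | Not necessarily an AE | Recorded | Recorded under 7.2.1.2.6 |
| Lack of efficacy only, loss of 15 letters or less, not judged relevant | Not necessarily an AE | Recorded | None |

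Protocol 8.2.1.1 lists BCVA among the ophthalmological evaluations, so 7.2.1.2.6 reaches BCVA loss as well as imaging findings. Only in the last row does the result rest on the two sections alone.

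**Step 5. Check the existing categories.** The lowest category in SAP 14 is a loss of 15 letters or more, while the AESI needs more than 15. They differ at exactly 15 letters, so a new table needs its own row for more than 15.

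**The case against.** The strongest reply has four parts.

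- **The AE conflict is thin.** Protocol 7.2.1.2.1 is a permissive general definition and 7.2.1.2.5 is a specific instruction. Recording satisfies both. This stands. A reader might infer that two sites could both comply and still record differently. The documents do not support that, because a site that omits the worsening departs from 7.2.1.2.5, even though it could point to 7.2.1.2.1.
- **Losses of 5 to 15 letters are not left without cover.** A reader might infer that a subject withdrawn in this range would reach no summary table. That is too strong. Protocol 7.2.1.2.6 covers clinically relevant BCVA change, and the withdrawal provision in 5.3.2 applies to progression already assessed as clinically significant. It is hard to see such a loss being judged not clinically relevant, and once recorded it enters the Safety-set AE tables. This stands too.
- **Early stoppers may contribute more than Visits 3 and 4.** A reader might infer that those two visits are all the BCVA they have. Protocol 8.2.3 and 8.2.4 provide end-of-treatment and follow-up assessments for those who stop only the agent, and Visit 5 may fall on Day 21. Withdrawal of consent ends all procedures, and the sponsor and investigator may agree to forgo follow-up.
- **The plan already discloses the values.** In a study of about 30 subjects, a full ITT listing is real disclosure, Listing 16.2.3.2 shows exclusions from the analysis sets, and SAP 8 permits other sets. All true, but a listing does not give the reader a count of subjects who lost vision, and SAP 24 plans no BCVA table on a wider set.

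**Conclusion.** The point holds and is minor. The firm part is the analysis set: 0 of 4 post-baseline BCVA summaries include subjects who stop before 3 weeks, and the route out through Protocol 5.3.2 is tied to the outcome. The BCVA summaries can therefore look more favourable than the experience of all treated subjects. That direction assumes that at least some early stoppers leave because of vision loss. Its size cannot be estimated, and the 5 subjects between 30 and 25 should not be read as expected progressions.

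The AE wording is a smaller, supporting point. The two sections are inconsistent as written, but the remaining gap is worsening that is due only to lack of efficacy, falls short of the AESI threshold and is not judged clinically relevant. SAP 1 names Clarification Memorandum #1, which is not among the documents and may already address the recording rule.

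**What to change.** 1. Add to SAP 24 a Safety-set table of the number and percentage of subjects with BCVA loss from baseline of at least 5, at least 10 and more than 15 letters. Count visits on study agent separately from visits after stopping the agent or after starting other wet AMD therapy, so that off-treatment and post-standard-of-care values are not mixed in. State how many treated subjects have no post-baseline BCVA.
2. Reconcile Protocol 7.2.1.2.1 and 7.2.1.2.5 to one recording rule for wet AMD worsening, applied at all sites. This review does not say which. Leave the clinical-relevance rule in 7.2 and 7.2.1.2.6 as it is.
3. Optionally, show disease worsening as its own discontinuation reason in SAP 10, where it would now fall under AEs or other.

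Cost: one descriptive table from BCVA, dosing dates and concomitant therapy already collected, plus a clarification memo or a one-sentence amendment. An any-visit count over up to 8 visits will pick up some measurement variation, so it should be read descriptively without a test. Depending on the rule kept, more AEs may be reported.

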7.2.1.2.2 Serious Adverse Event

An SAE is defined for this protocol as any AE that meets one or more of the following criteria:

- A. A death (CTCAE Grade 5 event) occurring during the study, whether or not considered treatment-related;
- B. A life-threatening event (CTCAE Grade 4);
- C. An event requiring inpatient hospitalization or prolonged hospitalization due to the adverse event;
- D. An adverse event resulting in a significant, persistent, or permanent change, impairment, damage or disruption in the participant’s body function or structure, physical activities or quality of life;
- E. An event that otherwise required a medical or surgical intervention to preclude permanent impairment or damage (excluding unrelated elective or cosmetic procedures).

7.2.1.2.3 Grading Severity of Adverse Events

The investigator must grade the severity of all reported adverse events into one of the following five (5) categories:

- Grade 1 (Mild)
- Grade 2 (Moderate)
- Grade 3 (Severe)
- Grade 4 (Life-Threatening)
- Grade 5 (Death)

The standardized CTCAE severity grading scales for the specific type of adverse event reported must be used when a matching CTCAE term is available. The highest severity grade experienced for the event should be reported. The initial severity grading may be updated in follow-up reports if the maximum grade changes to a higher level. The CTCAE grading scale should be used according the following guidelines.

Grade 1 (Mild)

Transient (< 48 hours) or mild discomforts, no or minimal medical therapy or intervention required, hospitalization not necessary, no or little limitation in normal activities, nonprescription or single-use prescription therapy may be employed to relieve symptoms (e.g., aspirin for simple headache, acetaminophen with codeine for post-surgical pain). Mild adverse events may be listed as expected consequences of the

therapy for any given protocol, and standard supportive measures for such an expected event do not necessarily elevate the event to a higher grade.

Grade 2 (Moderate)

Mild to moderate limitation in activity, some assistance may be needed; possibly none but usually minimal intervention/therapy required, hospitalization possible.

Grade 3 (Severe)

Marked limitation in activity, some assistance usually required; medical intervention/therapy required; hospitalization possible or likely.

Grade 4 (Life-Threatening)

Extreme limitation in activity, significant and immediate assistance required; significant medical/therapy intervention required to prevent loss of life; hospitalization, emergency treatment or hospice care probable. This grade is used when the subject was, in the view of the investigator, at substantial risk of dying at the time of the adverse event or it was suspected that use or continued use of the study agent would have resulted in the subject's death.

Grade 5 (Death)

Death related to AE.

